### 5.1. INCLUSION CRITERIA

To be eligible for inclusion into this study, each patient must fulfil the following inclusion criteria.

1. Male and female patients aged 18-45 years, inclusive;
2. New-onset T1D (1st IMP dose within 100 days from 1st insulin administration);
3. Positive for at least one diabetes-related auto-antibody (anti-GAD; IAA, if obtained within 10 days of the onset of insulin therapy; IA-2 antibody; ZnT8);
4. Require, or has required at some time, insulin therapy through multiple daily injections (**MDI**) or Continuous Subcutaneous Insulin Infusion (**CSII**);
5. Fasting C peptide  $\geq 0.205$  nmol/L on two occasions;
6. Patient able to comply with all protocol procedures for the duration of the study, including scheduled follow-up visits and examinations;
7. Patients who have given written informed consent prior of any study-related procedure not part of standard medical care.

### 5.2. EXCLUSION CRITERIA

Patients who meet any of the following criteria are NOT eligible for inclusion in the study.

1. Any other chronic disease, including type 2 diabetes, apart from autoimmune hypothyroidism requiring thyroid hormone replacement only; patients with severe (myxedema) disease potentially requiring immunosuppressive therapy will be excluded;
2. Moderate to severe renal impairment as per estimated Glomerular Filtration Rate (**eGFR**) 60 mL/min/1.73 m^2, as determined using Chronic Kidney Disease Epidemiology Collaboration (**CKD-EPI**) creatinine equation (see [Appendix 14.4.3](#));
3. Hepatic dysfunction defined by increased ALT/AST  $> 3 \times$  upper limit of normal (**ULN**) **and** increased total bilirubin  $> 3$  mg/dL [ $> 51.3$   $\mu$ mol/L];
4. Hypoalbuminemia defined as serum albumin  $< 3$  g/dL;
5. QTcF  $> 470$  msec;
6. A history of significant cardiovascular disease/abnormality
7. Occurrence of an episode of ketoacidosis or hypoglycemic coma in the past 2 weeks;
8. Known hypersensitivity to non-steroidal anti-inflammatory drugs;
9. Concomitant treatment with drugs metabolized by CYP2C9 with a narrow therapeutic index [i.e., phenytoin, warfarin, sulphonylurea hypoglycemics (e.g. tolbutamide, glipizide, glibenclamide/glyburide, glimepiride, nateglinide) and high dose of amitriptyline ( $> 50$  mg/day)];
10. Previous (within 2 weeks prior to randomization) and concomitant treatment with antidiabetic agents as metformin, sulfonylureas, glinides, thiazolidinediones, exenatide, liraglutide, DPP-IV

inhibitors, SGLT2-inhibitors or amylin, or any medications known to influence glucose tolerance (e.g.  $\beta$ -blockers, angiotensin-converting enzyme inhibitors, interferons, quinidine antimalarial drugs, lithium, niacin, etc.);

11. Past (within 1 month prior to randomization) or current administration of any immunosuppressive medications (including oral, inhaled or systemically injected steroids) and use of any investigational agents, including any agents that impact the immune response or the cytokine system;
12. Significant systemic infection during the 4 weeks before the first dose of the study drug (e.g., infection requiring hospitalization, major surgery, or IV antibiotics to resolve; other infections, e.g., bronchitis, sinusitis, localized cellulitis, candidiasis, or urinary tract infections, must be assessed on a case-by-case basis by the investigator regarding whether they are serious enough to warrant exclusion);
13. Hepatitis A (IgM), hepatitis B (not due to immunization), hepatitis C and HIV positive serologic status Serologic evidence of current infectious liver disease (hepatitis A, B, or C), including ant hepatitis A virus (immunoglobulin M), hepatitis B surface antigen, or ant hepatitis C virus and HIV;
14. Pregnant or breast feeding women. Unwillingness to use effective contraceptive measures up to 2 months after the end of study drug administration (females and males). Effective contraceptive measures include a hormonal birth control (e.g. oral pills, long term injections, vaginal ring, patch); the intrauterine device (IUD); a double barrier method (e.g. condom or diaphragm plus spermicide foam).

### **5.3. ASSIGNMENT OF PATIENT NUMBER**

At the screening visit each patient will be assigned a unique sequential patient number by an Interactive Response System (IRS). This number will be used for identification throughout the study and will not be used for any other participant.

If a patient is dropped from the study for any reason, the patient's randomization number will not be reassigned.

## 6. STUDY MEDICATION

### 6.1. PRESENTATION, STORAGE, PACKAGING AND LABELING OF THE INVESTIGATIONAL MEDICINAL PRODUCT

#### 6.1.1. Presentation of Investigational Medicinal Product

In this study the Investigational Medicinal Product (IMP) will be either ladarixin OR matched placebo. It will be provided as hard gelatine capsules for oral administration, with the following composition:

Composition for each unit (capsule)

Batch release certificate will be provided together with the IMP.

#### 6.1.2. Manufacturing, Packaging and Labelling of IMP

Capsules will be manufactured by PPD will manage the labelling and packaging of capsules in blisters to obtain the Patient Kit.

The study medication will be provided as a Patient Kit, containing 2 Treatment wallets, covering the treatment period of 1 cycle. Each Treatment wallet will contain treatment 28 capsules.

All labels will be prepared to meet local regulatory requirements. Details of packaging and labelling are reported in [Appendix 14.1](#).

#### 6.1.3. Supply, Storage and Handling of IMP

An appropriate number of packages will be initially sent to the site as soon as all essential documents and regulatory/ethics approvals have been obtained. IMP re-supply will be planned on demand, according to enrolment rate.

The IMP must be kept at a temperature not exceeding 30°C and must not be frozen.

A temperature probe will accompany the drug on shipment. Temperature range reached during shipment will be verified on receipt at site, so that potential stability concerns during shipment can be investigated and appropriate action taken.

Once received at the site, the Pharmacist (or designee) will check the package for accurate delivery and acknowledge receipt; any deviations from expected package content (inconsistency, damages) should be immediately reported to Dompé (or appointed CRO) and the use of the drug suspended until authorization for its continued use has been given by Dompé (or appointed CRO).

The IMP must be stored at site in a secure location, in a temperature controlled room. Temperature records must be available for the CRA to review at monitoring visits; any deviations from the recommended storage conditions should be immediately reported to Dompé (or appointed CRO) and

the use of the drug suspended until authorization for its continued use has been given by Dompé (or appointed CRO).

#### 6.1.4. Blinding

Appearance, including packaging and labelling, of the IMP (capsules, packaging) will not allow to recognize actual treatment (either ladarixin or placebo).

During the trial, blinding will be broken by the Investigator for emergency purposes only, where knowledge of the blinded treatment could influence further patient care. In addition, safety reports will be unblinded, as per regulatory requirements.

Study blind will be broken after database lock.

### 6.2. IMP DISPENSATION

The IMP will be dispensed quarterly only by the Pharmacist (or authorized designee at site).

The IMP will be dispensed via IRS as Patient Kits during the Randomization Visit and then during the Visits scheduled at the end of the 3rd (Week 11), 6th (Week 23) and 9th (Week 35) treatment cycles, after check of inclusion/exclusion criteria (at Randomization) and discontinuation criteria at the scheduled visits \* (see [Section 6.4.2](#)).

A total number of 13 Patient IMP Kits will be dispensed to each randomized subject as follows:

- at Randomization Visit dispensed 3 Patient Kits for the Cycles 1, 2 and 3
- at Week 11 Visit dispensed 3 Patient Kits for the Cycles 4, 5 and 6
- at Week 23 Visit dispensed 3 Patient Kits for the Cycles 7, 8 and 9
- at Week 35 Visit dispensed 4 Patient Kits for the Cycles 10, 11, 12 and 13

[\* Results of ALT/AST, bilirubin, creatinine, albumin, ECG readings and pregnancy results should be made available by local laboratory in time to allow Patient Kits dispensation as soon as possible during the visit. If this expedite timing cannot be achieved, Patient Kits might be delivered to patient named address by a selected courier (CRO to support shipment). Study drug dispensation will be performed as soon as possible after check of discontinuation criteria.]

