### 2.5.1. Selection of dose and treatment schedule in the study

The dose and treatment schedule proposed in this phase 2 study is 400 mg oral ladarixin twice a day for 13 cycles of 14 days on - 14 days off. However, ladarixin will NOT be administered to trial patients for longer than 3 months (3 cycles) before chronic toxicity data in rats and dogs have been deemed sufficient by the FDA to support ladarixin exposure up to one year.

The oral route has been selected based on the very good oral bioavailability of ladarixin, the long half-life and its good tolerability when given by this route.

The 400 mg b.i.d. dosage is supported by both preclinical studies and efficacy/safety results from phase 2 clinical study CCI in T1D adult patients. Actually, this dose was already established to be safe in phase 1 clinical studies in adult male healthy subjects.

The resulting average steady state plasma concentration of the ladarixin unbound fraction should ensure full inhibition of PMN migration, considering that the in vitro IC50 is in the range of 1 ng/mL.

A treatment of 14 days in a regimen of 14-days on and 14-days off resulted beneficial in the phase 2 study CCI, in line with the initial observations in NOD mice. In fact, in ladarixin-treated NOD mice with recent onset-diabetes the efficacy of the compound was clearly more pronounced within the 14 days after treatment interruption (in these animals, the average of non-fasting glycemia was below 200 mg/dl) whereas blood glucose concentrations tended to progressively increase in 77% of remission NOD mice at later time after treatment discontinuation, suggesting that neutrophil recruitment as well the cross-talk with the other immune cells in the pancreas could restart after 14 days of ladarixin treatment discontinuation. This was further supported by the evidence that a second cycle of ladarixin treatment in NOD-mice with diabetes recurrence was able to reverse again diabetes in 67% of mice, thus supporting the concept that repeated cycles of treatment are necessary and appropriate for the management of the chronic condition.

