### 2.5.3. Risk - benefit evaluation

#### 2.5.3.1. Risk related to the ladarixin

Results from preclinical studies support the level of drug exposure planned in this study.

Phase 1 and 2 clinical experience with doses as high as that planned in this study provides evidence of the safety of ladarixin. The safety was confirmed in the phase 2 trials; indeed, no safety concerns were raised either in elderly patients who were on several concomitant medications due to chronic disease, or in patients with new-onset T1D. No SUSAR or death occurred and all the AEs encountered were mild to moderate in intensity.

The available toxicity data supports 3 months of continuous treatment in humans. Six-month and 9-month chronic studies in rats and dogs (respectively) will be conducted, according to ICH guideline M3(R2), in order to support ladarixin administration up to 12 months. Even if the protocol anticipates, and remains structured for, 1 year of treatment (13 cycles), patients will not be treated longer than 3 months until such additional chronic toxicology data in rats/dogs have been reviewed by the FDA.

[Any possible risk derived from the administration of ladarixin in the specific population involved in this study will be minimized by integrated monitoring which includes clinical observations, laboratory tests and ECG readings scheduled at pre-planned interval (see Section 6.4.2 - discontinuation criteria for details)].

Ladarixin inhibits enzyme CYP2C9 and may affect plasma levels of those drugs that are metabolized by this system. Restrictions of use and monitoring procedures (see Section 6.5.2 for details) will limit any possible risks derived from potential metabolic interactions.

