### 6.3. DOSE, ROUTE AND SCHEDULE OF IMP ADMINISTRATION

Ladarixin will be administered orally at the dose of 400 mg twice a day for 3 cycles of 14 days on / 14 days off. Placebo will be administered with the same treatment schedule. Administration will be extended up to 12 months (13 cycles) **only after additional chronic toxicity data support such longer treatment.**

The two daily doses will be administered at about 12hour interval (morning and evening; ideally between 6:30/11:30 and 18:30/23:30). At each administration, 2 capsules will be swallowed with a glass of water, at least 2 hours apart from breakfast or dinner.

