After having confirmed the patient has not developed a condition that prevents his/her continuing participation into the study\*, he/she will be provided with the Patient Kits matching his/her randomization number, together with the Patient Diary, according to the schedule reported below: (see also section 6.2).

- at Week 11 Visit dispensed 3 Patient Kits for the Cycles 4, 5 and 6
- at Week 23 Visit dispensed 3 Patient Kits for the Cycles 7, 8 and 9
- at Week 35 Visit dispensed 4 Patient Kits of IMP for the Cycles 10, 11, 12 and 13

\* Results of ALT/AST, bilirubin, creatinine, albumin, ECG readings and pregnancy results should be made available by local laboratory in time to allow dispensation of Patient Kits as soon as possible during the visit. If this expedite timing cannot be achieved, Patient Kits might be delivered to patient named address by a selected courier (CRO to support shipment).

The administration of the IMP (date/time for each administration, number of capsules) will be recorded by the patient in the Patient Diary which data will be checked by the Investigator during the next study visit.

It is the responsibility of the Investigator (or designee) to check the information the patient will insert in the Patient Diary to ensure correct intake of the IMP. The Investigator will remind, and make sure patient still fully understands any appropriate treatment related information.

The Patient Kits containing all the blisters, either unused or empty, will be returned to and checked by the Investigator during the next study visit.

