** sensor to be positioned at least 10 days before the scheduled visits**

(X) CGM sensor implantation can occur at Screening Visit and Week 23 Visit if the visit is scheduled 14-10 days before Baseline and before Week 26 respectively

** Dispensation of IMP (Patient Kits) must occur ONLY after check of inclusion/exclusion criteria (at the Randomization Visit) and of discontinuation criteria (at the Visits performed at the end of the 3rd, 6th, 9th treatment cycles). Results of ALT/AST, bilirubin, creatinine and albumin, ECG reading and pregnancy results should be made available by the local laboratory in time to allow Patient Kits dispensation as soon as possible during the visit. If this expedite timing cannot be achieved, Patient Kits might be delivered to patient named address by a selected courier (CRO to support shipment). As per treatment discontinuation criteria, no IMP will be dispensed in the case: QTcF is either > 500 msec or has increased by > 60 msec from baseline measurement on two consecutive ECG readings taken 1 hour apart; the patient develops any significant cardiovascular disease/abnormality, renal (eGFR <60mL/min/1.73 m^2) or hepatic (increased ALT/AST > 3 x ULN and increased total bilirubin > 3mg/dL [ $>51.3 \mu\text{mol/L}$ ]) dysfunction, hypoalbuminemia (serum albumin <3 g/dL), significant systemic infection that must be assessed on a case-by-case basis by the investigator regarding whether they are serious enough to warrant discontinuation, ketoacidosis or hypoglycemic coma; a female patient has become pregnant.**

** Telephone calls will be scheduled on a regular basis to ensure optimization of metabolic control. It is expected that patients are contacted at least every 2 to 3 weeks during study participation. A telephone call will be anyway scheduled in the 2 weeks before a planned visit.**

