# PPD

## 6. Evaluation of Treatment Compliance and Exposure

### 6.1 Compliance to study treatment regimen

Descriptive analyses of the following parameters will be presented by treatment group for each cycle and during the entire treatment period:

- from IMP dispensation form
  - number of capsules dispensed;
- from IMP accountability form
  - number of returned blisters;
  - number of capsules taken;
  - number of returned unused capsules;
  - IMP intake compliance, ON -treatment period compliance (only by cycle);

Patients are instructed to receive study treatment (either ladarixin or placebo) as follows:

- 400 mg b.i.d (2 capsules at each administration, twice per day);
- for 13 cycles, each lasting 28 days;
- each cycle is composed by 14 consecutive days on-treatment and 14 consecutive days off-treatment.

Calculation of compliance to treatment regimen must consider not only the amount of treatment intake, but also the correct alternation between period “ON” and period “OFF” and their duration. To assess the overall compliance to treatment regimen, the following 3 criteria will be taken into account:

- Compliance to IMP intake;
- Compliance to duration of period “ON” (period of the cycle when the patient is ON treatment);
- Compliance to duration of period “OFF” (period of the cycle when the patient is OFF treatment).

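### The 3-cycle dosing hold pending chronic toxicology review is stated in four protocol sections but is missing from the dispensing, discontinuation, treatment-period, flow-chart and synopsis text, and its release condition is worded four ways

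*Protocol*

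**What the plan says.** **Where the hold appears.**
- Protocol 2.5.1: "ladarixin will NOT be administered to trial patients for longer than 3 months (3 cycles) before chronic toxicity data in rats and dogs" have been judged sufficient by the FDA.
- Protocol 2.5.3.1: "patients will not be treated longer than 3 months until such additional chronic toxicology data in rats/dogs have been reviewed by the FDA". The same sentence acknowledges that the protocol is still laid out for a year of treatment.
- Protocol 3.3: dosing runs for 3 months and goes on to a year only once the FDA has given notice that the longer exposure is acceptable.
- Protocol 6.3 (dose, route and schedule): the schedule is 3 cycles, with extension to 13 only after further chronic toxicity data support it. The FDA is not named.

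**Where it does not appear.**
- Protocol 6.2: "A total number of 13 Patient IMP Kits will be dispensed to each randomized subject as follows". The list runs from 3 kits at randomization to the last entry, "at Week 35 Visit dispensed 4 Patient Kits for the Cycles 10, 11, 12 and 13".
- Protocol 6.4.1 foresees no schedule change other than discontinuation. The criteria in 6.4.2 all concern the individual patient.
- Protocol 7.3: 12 further cycles follow the first unless a reason in 6.4.2 applies, and "at Week 11 Visit dispensed 3 Patient Kits for the Cycles 4, 5 and 6".
- Appendix 14.2, footnote 5 (repeated under the flow chart in SAP 3.2): "Dispensation of IMP (Patient Kits) must occur ONLY after check of inclusion/exclusion criteria (at the Randomization Visit) and of discontinuation criteria".
- The synopsis (study design, investigational product and treatment-period paragraphs) gives 13 cycles without mentioning the hold.
- SAP 6.1 describes patients as instructed to take treatment "for 13 cycles, each lasting 28 days".

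**The concern.** The hold is a safety restriction. Protocol 2.2 and 2.5.3.1 say the available animal data support 3 months of continuous treatment, with longer rat and dog studies to follow. The restriction takes effect when cycle 4 drug would be handed over, at the Week 11 visit. The sections that govern that visit neither mention the hold nor refer to 6.3. If clearance has not arrived, the protocol gives a site two incompatible instructions and no procedure for choosing between them.

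There is also a reporting question. A patient kept at 3 cycles because of the hold has not met any criterion in 6.4.2, so it is unclear whether that patient has discontinued treatment. Some SAP derivations depend on the answer.

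**Working it through.** **1. Reproduce the plan's own counts.** Inputs: kits per visit (Protocol 6.2), 2 capsules twice a day (6.3), 14 dosing days per cycle, 56 capsules per kit (Appendix 14.1), 728 capsules in total (SAP 6.1.1.1), 182 ON days (SAP 6.1.2.1).
- Kits: 3 + 3 + 3 + 4 = 13, as stated.
- Capsules per kit: 2 × 2 × 14 = 56, as stated.
- Total capsules: 13 × 56 = 728, as stated.
- Total dosing days: 13 × 14 = 182, as stated.

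**2. Split at the hold.**
- Within the hold: 3 kits, 3 × 56 = 168 capsules, 3 × 14 = 42 dosing days.
- Beyond the hold: 10 kits, 728 − 168 = 560 capsules, 182 − 42 = 140 dosing days, which is 10/13 = 77% of the regimen.

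These figures measure how much of the regimen the conflicting passages cover. They do not measure drug given without clearance.

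**3. What the Week 11 procedure checks.** Under 6.2, 7.3 and footnote 5, cycle 4–6 kits follow a check of the 6.4.2 criteria: QTcF, cardiovascular, renal, hepatic, albumin, pregnancy, infection, ketoacidosis or hypoglycemic coma. A patient who passes is given the kits. Toxicology clearance is not in the list.

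**4. Compare the release conditions.**
- 2.5.1: the FDA has found the data sufficient.
- 2.5.3.1: the FDA has reviewed the data.
- 3.3: the FDA has given notice that longer exposure is acceptable.
- 6.3: the data support longer treatment, and no authority is named.

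Review is not the same as acceptance. The wording in 2.5.3.1 or 6.3 could be met while that in 2.5.1 or 3.3 is not.

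**5. Effect of discontinuer status in the SAP.** Take a patient who takes all of cycles 1–3 on schedule and is then held for good. Cycle 3 starts on day 57, so the last intake is day 57 + 13 = day 70.
- ON-period compliance (SAP 6.1.2.1), counted as a discontinuer: expected 14 × 3 = 42 days, so 42/42 = 100%.
- ON-period compliance against the full-course expectation: 42/182 = 23%.
- Adverse-event period (SAP Table 5), counted as a discontinuer: events after day 70 fall in follow-up.
- Adverse-event period, not a discontinuer: events count as on treatment until the Month 12 visit, nominally day 52 × 7 = 364. About 364 − 70 = 294 days change category.
- Intake compliance (SAP 6.1.1.1) divides by capsules dispensed, so it is 168/168 = 100% and does not show that 10 cycles were not given.

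**The case against.** The strongest reply is that the hold is hard to miss. It appears four times, including in 6.3, the dosing section that directly follows 6.2, and 2.5.3.1 says openly that the 13-cycle layout stands although the cap applies. A site reading all of Section 6 would meet it. This stands, and it rules out any suggestion that the hold is confined to background text. It does not remove the conflict: adjacent sections then give different instructions, and 7.3 and the flow chart refer the site to 6.4.2, not to 6.3. The synopsis makes later kits depend on criteria for drug administration, but that sentence follows the list of discontinuation checks and does not mention toxicology.

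A reader might infer that cycles 4–13 would go to every patient without clearance. The documents do not support that. Patients meeting a 6.4.2 criterion get no further kits. Kits are issued through the interactive response system, which may or may not block release; the documents are silent. Nothing shows that any patient reached Week 11 before clearance.

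A reader might also infer that the SAP cannot reveal 3-cycle patients. It partly can: 6.1.5 counts cycles started, 5.5 tabulates reasons for stopping drug, 6.2 reports exposure, and Protocol 6.4.2 requires the primary reason to be recorded. What is missing is this particular cause and a rule for its status.

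Finally, a reader might try to calculate how far the planned 35-point difference would be diluted. No held fraction is given, and the earlier trial's 68.2% against 53.3% in this C-peptide stratum is a Week 26 result (p=0.361), whereas 35 points is a Month 12 assumption. No dilution figure can be supported.

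**Conclusion.** The inconsistency holds. Four sections cap dosing at 3 cycles pending toxicology review. The dispensing, discontinuation, treatment-period, flow-chart and synopsis passages provide for 13 cycles without that condition, and the release condition has four wordings. The conflict covers 77% of the regimen. Whether it led to any dosing beyond the hold cannot be determined from the documents.

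This rests on the text alone, with no assumption about effect size or power. No view is taken on which dosing rule is right. Enrolment was stopped early and SAP version 3.0 makes all analyses descriptive, so the protocol repair may now matter mainly for the record. The SAP point still bears on the compliance and adverse-event tables, if any patient was held.

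**What to change.** **Protocol.** The sponsor must reconcile 2.5.1, 2.5.3.1, 3.3 and 6.3 with 6.2, 6.4.1–6.4.2, 7.3, footnote 5 and the synopsis, so that all state one consistent rule and one release condition of the sponsor's choosing. The text should say how a patient who reaches Week 11 before release is handled.

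**SAP.** Add a flag for patients whose dosing was held or ended at 3 cycles for this reason. State whether they count as treatment discontinuers for ON-period compliance and for Table 5, and show the cause in the disposition output alongside the reasons already listed in 5.5. Bring 6.1 and the flow-chart footnote in 3.2 into line with the reconciled protocol.

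**Cost.** Wording changes across the protocol sections named and the synopsis, one statement on Week 11 handling, and one SAP flag with its derivation rule and table line. No new visits, assessments or patients.
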